2.0	General (Rationale)	NDMA analyses will be based on arithmetic means instead of geometric means. Blinded review of the bioanalytical data revealed that a large number of urine and plasma samples for NDMA were below the lower limit of quantification (LLOQ). For multiple subjects, all samples from 1 or more study periods were below the LLOQ. As zero values cannot be log-transformed for geometric mean analyses, these periods would have been removed from analysis. Furthermore, as analyses are paired, these subjects would have been removed from analyses. Utilizing arithmetic mean will allow data from all subjects and all periods to be used in the planned analysis. Ranitidine and DMA analyses will remain the same (i.e. utilizing geometric means).
	7.3.1	Analysis of urine concentrations Analysis of NDMA urine 24-hr excretion will be performed using arithmetic means instead of geometric means.
	7.3.2	Plasma pharmacokinetics Descriptive statistics for plasma PK parameters of NDMA will be calculated using arithmetic means.

1. Introduction

This document outlines the proposed statistical methods for data analysis of data collected from Protocol ‘SCR-010 Clinical study to investigate the urinary excretion of N-nitrosodimethylamine (NDMA) after ranitidine administration’.

2. Objectives

The following analysis plan provides the framework for the summarization of the data from this study. The analysis plan may change due to unforeseen circumstances but will be finalized prior to database lock. Any changes made after the database lock will be documented and justified in the clinical study report.

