6.1 Handling of Missing and Incomplete Data

The following imputation of missing values will be done:

- PK measurements (urine or plasma) below the quantification limits will be considered equal to zero for all analyses.
- Missing PK data (e.g., skipped plasma sample collected or uncollected urine voids) will not be imputed.

7. General Statistical Considerations

All data will be presented in data listings. Data from subjects excluded from an analysis population will be presented in the data listings, but not included in the calculation of summary statistics.

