7.3.2 Plasma Pharmacokinetics

The following PK parameters will be determined for NDMA, DMA, and ranitidine (only Treatments A and C) for each subject based on all available concentration-time points:

- **AUC from time 0 to the sampling time corresponding to the last quantifiable concentration (C_{last}) (AUC_{0-t})**

AUC_{0-t} will be calculated according to the linear trapezoidal rule from 0 h to the last quantifiable concentration after drug administration.

- **AUC from time 0 extrapolated to infinity (AUC_{0-inf})**

AUC_{0-t} will be extrapolated to infinity from the AUC from time 0 to the sampling time corresponding to the last quantifiable concentration plus the last quantifiable concentration divided by K_{el} , as follows:

$$AUC_{0-inf} = AUC_{0-t} + C_{last}/K_{el}$$

- **Maximum concentration (observed peak drug concentration) (C_{max})**

C_{max} will be read directly from the observed concentrations.

- **Time at which C_{max} occurs (T_{max})**

T_{max} will be read directly from the observed concentrations as the blood sampling time corresponding to C_{max} . The earlier time will be reported in cases where the same C_{max} value is observed for a subject at multiple timepoints

- **Terminal half-life ($t_{1/2}$)**

The terminal half-life will then be calculated using the elimination rate constant as:

$$t_{1/2} = \ln(2)/K_{el}$$

- **K_{el}**

The terminal elimination rate constant, which will be determined from the terminal slope of the log-concentration curve using linear regression

The PK parameters will be analyzed using noncompartmental methods based on actual sampling times. Serum concentrations below the limits of quantification will be set to zero for the purpose of this analysis (see Section 6). AUC_{0-inf} , $t_{1/2}$, and K_{el} for each analyte and subject will only be

included if the subject has 3 or more concentration values on the terminal portion of the pharmacokinetic curve and with an adjusted coefficient of determination (R^2) greater than 0.80.

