AUC_{0-inf} and C_{max} will be compared with either low nitrite/NDMA meals (comparison between Treatments A and B, respectively) or high nitrite/NDMA meals (comparison between Treatments C and D, respectively) using a paired t-test. Normality assumption will be verified using the Shapiro-Wilke test for normality. If the assumption is not valid, the data will be log-transformed, and then tested for normality. Homogeneity of variances will be verified using Lavene's test. If the data in its original or transformed form does not meet the t-test assumptions, a Wilcoxon signed-rank test will be used for the comparison rather than a paired t-test.

These PK parameters will be summarized using descriptive statistics (number of subjects, mean [arithmetic for NDMA; geometric for DMA and ranitidine], SD, coefficient of variation [CV], median, minimum, and maximum) for NDMA, DMA, and ranitidine.

All parameters will be calculated using R software. Mean and individual concentration-time profiles will be presented in graphs.

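### SAP 7.3.2 sends non-normal plasma data to a log transform with no exception for NDMA, whose below-LLOQ values are set to zero, so the Cmax step cannot be run as written and its handling of zeros is left open

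*SAP*

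**What the plan says.** SAP 7.3.2 compares AUC0-inf and Cmax between treatments A and B and between C and D with a paired t-test, preceded by a Shapiro-Wilk check. When that check fails: "If the assumption is not valid, the data will be log-transformed, and then tested for normality". A Levene check of equal variances follows. The last resort is: "If the data in its original or transformed form does not meet the t-test assumptions, a Wilcoxon signed-rank test will be used". The paragraph names no analyte. Ranitidine parameters are derived only for A and C, so in practice it governs NDMA and DMA.

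The rule for unquantifiable values is in SAP 6.1, "PK measurements (urine or plasma) below the quantification limits will be considered equal to zero for all analyses", and 7.3.2 repeats it: "Serum concentrations below the limits of quantification will be set to zero for the purpose of this analysis". Cmax is read directly from the observed concentrations.

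The version 2.0 rationale in the SAP Change Log reports that many urine and plasma NDMA samples were below the LLOQ. It adds: "For multiple subjects, all samples from 1 or more study periods were below the LLOQ". It then gives the consequence of logging: "As zero values cannot be log-transformed for geometric mean analyses, these periods would have been removed from analysis", and "Furthermore, as analyses are paired, these subjects would have been removed from analyses". For 7.3.2 the log lists a change to the descriptive statistics only. For urine, SAP 7.3.1 now analyses NDMA untransformed and goes directly to the Wilcoxon signed-rank test if an assumption fails.

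**The concern.** Version 2.0 was written to stop the log scale from discarding NDMA periods, but the plasma test kept a log step. The conflict lies within the current text: 6.1 and 7.3.2 create zeros for NDMA, and 7.3.2 then logs them when normality fails. The Change Log matters here only because it shows that the sponsor knew of the problem.

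At stake is the NDMA Cmax comparison. If zero pairs are deleted, the t-test runs on a subset selected by outcome. Under a true increase, that subset has lost many pairs that go from unquantifiable on placebo to quantifiable on ranitidine. If the zeros are handled some other way, the SAP does not say which, and the choice would be made with the data in hand.

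**Working it through.** **The plan's own figure.** The SAP gives no power for the plasma test. Its urine calculation (SAP 3.2: ratio 2, CV 100%, one-sided 0.05, 14 completers, at least 90% power) reproduces:
- Effect: ln 2 = 0.693.
- SD of the paired log difference: sqrt(ln(1 + 1²)) = 0.833.
- Noncentral t at n = 14: power 0.904.
- Enrolment: 14 / (1 − 0.20) = 17.5, rounded up to 18.

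**The logic for one subject.**
- All plasma NDMA samples in a period below the LLOQ are set to 0, so Cmax = 0.
- ln(0) is minus infinity. A log difference with one zero is infinite, and with two zeros it is undefined.
- Neither the second Shapiro-Wilk test nor the t-test can be computed until someone decides what to do with that pair.
- AUC0-inf does not reach this point. It needs at least 3 terminal concentrations with adjusted R² above 0.80, which an all-zero period cannot supply.

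**Inputs for sizing.** From the SAP: 18 subjects, and the urine planning values (ratio 2, CV 100%, one-sided 0.05) borrowed for plasma. Assumed: lognormal Cmax, within-pair correlation 0.5, normality tested on paired differences, and the share of placebo periods with Cmax = 0. The documents give no such counts.

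**If pairs with a zero are deleted** (simulation of the 7.3.2 path without the Levene check, thousands of trials per column):

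| Placebo periods with Cmax = 0 | 20% | 40% | 60% |
|---|---|---|---|
| Shapiro-Wilk fails on raw differences | 57% | 49% | 50% |
| Pairs lost of 18 when it fails | 4.0 | 7.8 | 11.7 |
| of which zero on placebo, quantifiable on ranitidine | 3.1 | 5.3 | 6.3 |
| of which double-zero or reverse (by subtraction) | 0.9 | 2.5 | 5.4 |
| Retained pairs then pass normality on the log scale | 94% | 93% | 92% |
| Ratio in retained pairs (truth 2) | 1.84 | 1.73 | 1.60-1.64 |
| Overall power, 7.3.2 path | 88-89% | 80-81% | 62-68% |
| Overall power, signed-rank on all 18 pairs | 92-93% | 90-93% | 87-88% |

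Ranges are the spread over repeat simulations. It is widest at 60%, where only about 18 − 11.7 = 6.3 pairs remain. Because the retained pairs usually pass on the log scale, the signed-rank fallback is seldom reached.

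**Sensitivity.**
- At 5% and 10% of placebo periods, power is 92% and 91%, against 92% for signed-rank on all pairs.
- With a true ratio of 4, power is 100/100/96% at 20/40/60%, against 100%.
- With no true effect, losses are symmetric and the one-sided error stays at about 4-6%.

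**If a zero is treated as a failed assumption** and sends the test to signed-rank on all pairs, power is 92/92/88% at 20/40/60%, the same as using signed-rank throughout.

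**Levene.** A paired t-test needs approximately normal differences, not equal arm variances. With a true two-fold increase, Levene's test on the two arms rejects in 58/45/25% of trials at CV 30/50/100%, although the paired test is valid. Adding it to the path changes power little (89/82/69%).

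**The case against.** The strongest objection is that 7.3.2 never says zeros are deleted. Its last sentence sends the comparison to Wilcoxon when the data fail in original or transformed form. A vector containing log(0) has no usable transformed form, so Wilcoxon on all pairs is a natural reading, and on that reading nothing is lost. The Change Log sentence about removal concerns geometric mean analyses, not this test. This stands: the documents establish an unstated rule, not a bias that must occur.

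The sizes also rest on borrowed or assumed inputs. The Change Log gives no count and does not split all-unquantifiable periods by plasma and urine or by treatment. Section 7.3.2 states neither alpha nor sidedness for the plasma tests. This stands too, so the table is only an illustration.

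A reader might infer that the plan discards precisely the pairs with the clearest increase. The documents do not support that. Double-zero and reverse pairs would go as well. A double-zero pair also adds nothing to a standard signed-rank test, and a value just above the LLOQ need not be a large increase. What remains is that, under a true increase, zero-to-quantifiable pairs outnumber reverse pairs, so the net effect of deletion is toward no increase.

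Finally, plasma is exploratory and the listed plasma endpoint is AUC0-inf. That limits the consequence but does not make the step executable.

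**Conclusion.** The point holds as a defect of specification. For NDMA Cmax in a period with no quantifiable plasma sample, the log step in SAP 7.3.2 cannot be carried out as written, and the SAP does not say what replaces it. That conclusion needs no assumption beyond the occurrence of such periods.

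The consequence depends on the reading. Deleting zero pairs would pull the estimated ratio from 2 to about 1.84/1.73/1.6 and lower power to about 88/81/62-68% at 20/40/60% of placebo periods, under the assumptions listed. It would matter little at 10% or below, or with a four-fold effect. Routing zeros to the signed-rank test costs nothing. The two readings can give different answers on the same data, so one should be fixed beforehand.

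It should not be inferred that the primary result is affected or that false positives increase. Urinary NDMA is tested untransformed with its own Wilcoxon fallback, and type I error stays near 5% in every scenario run. The change should be made, but it concerns one exploratory comparison.

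**What to change.** In SAP 7.3.2:
- Exempt NDMA from the log step and keep it for DMA.
- State that NDMA Cmax is compared untransformed. If normality of the paired differences fails, the Wilcoxon signed-rank test is applied directly to all pairs, as in 7.3.1 for urine.
- Report, for A versus B and C versus D, how many pairs have a zero on placebo only, on ranitidine only, and on both.
- Delete the Levene condition for the paired comparison (minor).

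This does not recover AUC0-inf for all-unquantifiable periods, which the terminal-slope rule excludes whether or not the data are logged. The report should say so. The cost is a few sentences in the SAP, with no new data and no change to the primary analysis.

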**Primary Analysis**

**Pharmacokinetics:** Cumulative amount of NDMA excreted in urine over 24-hours is the primary PK parameter of interest. This will be determined by calculating cumulative amount excreted during specified intervals, and summarizing totals over a 24-h period. Similar approaches will be utilized for determining cumulative amount of DMA and ranitidine excreted in urine over 24-h.

Area under the curve and additional PK parameters from ranitidine, DMA, and NDMA plasma concentrations will be determined for each subject using non-compartmental methods. All parameters will be reported with standard descriptive statistics including the geometric mean and coefficient of variation. Calculation of PK parameters will be performed using actual sampling times.

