Cumulative amounts of DMA and ranitidine will be log-transformed. A mixed-effect analysis of variance (ANOVA) approach will be used for comparing arithmetic means (for NDMA) and geometric means (for DMA and ranitidine) looking at the effects of treatment, period, and sequence. For NDMA, testing will be one-sided at a 0.05 significance level, and a significant increase will be concluded if the lower bound of the one-sided 95% interval for the arithmetic mean difference excludes 0. For DMA and ranitidine, testing will be one-sided at a 0.05 significance level, and a significant increase will be concluded if the lower bound of the one-sided 95% interval for the geometric mean ratio excludes 1. The results will be transformed back to the original scale by exponentiation to provide treatment geometric means.

Normality assumption of the ANOVA will be verified using the Shapiro-Wilke test for normality and homogeneity of variances will be verified using Levene's test. If either assumption is not valid, a Wilcoxon signed-rank test will be used for the comparison rather than an ANOVA.

Individual and mean time course plots of NDMA, DMA, and ranitidine excreted over 24-hr will be evaluated for each treatment. All urine PK parameters will be summarized using descriptive statistics (number of subjects, mean, SD, coefficient of variation [CV], median, minimum, and maximum) for NDMA, DMA, and ranitidine. Individual time course plots will use actual sampling times. Treatment mean plots will use planned sampling times.

All calculations and the hypothesis testing will be done using R software.

Total fraction of the ranitidine dose excreted in urine ($Fe_{0-24, \text{ranitidine}}$) will be determined for Treatments A and C based on the cumulative amount of ranitidine excreted in urine over 24-h ($Ae_{0-24, \text{ranitidine}}$) divided by 300 mg. This will be calculated for each individual, summarized using descriptive statistics (number of subjects, mean, SD, CV, median, minimum, and maximum), and visualized graphically using box-and-whisker plots.

Renal clearance of ranitidine will be determined (only for Treatments A and C) by calculating the rate of excretion as the difference between the later and earlier compound level divided by the difference in times points (i.e., $[\text{amount}_{t_2} - \text{amount}_{t_1}] / [t_2 - t_1]$). The log-transform of the renal

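### SAP 7.3.2 summarises plasma DMA by geometric means but lets assumption tests choose the scale on which AUC0-inf and Cmax are compared, so test and summary may not match

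*SAP*

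**What the plan says.** **Urine DMA (SAP 7.3.1).** The scale is set in advance: "Cumulative amounts of DMA and ranitidine will be log-transformed". An increase is concluded if the lower one-sided 95% bound for the geometric mean ratio lies above 1. If Shapiro-Wilk or Levene's test fails, a Wilcoxon signed-rank test replaces the ANOVA.

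**Plasma DMA, summary (SAP 7.3.2).** The type of mean is fixed by analyte: "mean [arithmetic for NDMA; geometric for DMA and ranitidine". The Protocol Synopsis, under Primary Analysis, also asks for geometric means: "All parameters will be reported with standard descriptive statistics including the geometric mean and coefficient of variation".

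**Plasma DMA, comparison (SAP 7.3.2).** "AUC_{0-inf} and C_{max} will be compared with either low nitrite/NDMA meals" (A against B) or high-nitrite meals (C against D), "using a paired t-test. Normality assumption will be verified using the Shapiro-Wilke test for normality". Next comes "If the assumption is not valid, the data will be log-transformed, and then tested for normality", with Levene's test for equal variances. If neither scale passes, "a Wilcoxon signed-rank test will be used for the comparison rather than a paired t-test".

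The comparison sentence names no analyte. DMA is covered through the parameter list that opens the section: "The following PK parameters will be determined for NDMA, DMA, and ranitidine (only Treatments A and C"). Because ranitidine is measured only in A and C, the A-B and C-D comparisons can apply only to NDMA and DMA. Protocol 4.9.6.2 plans only descriptive statistics for plasma, so nothing there places plasma DMA on a log-scale test.

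**The concern.** Within section 7.3.2 the summary scale for DMA is fixed and the test scale is not. Each of the four plasma DMA tests (2 parameters x 2 meals) can end on any of three quantities:

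- a difference of arithmetic means;
- a ratio of geometric means;
- a signed-rank shift.

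A p-value for an arithmetic difference may then stand beside two geometric means. Low and high meals, AUC0-inf and Cmax, or plasma and urine DMA may be judged on different scales although readers will want to compare them. The choice rests on a normality test with at most 18 pairs, which often does not reject for log-normal data.

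What is at stake is how clearly an exploratory result can be read, plus a little power. The point concerns DMA only; NDMA has a separate problem with values set to zero.

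**Working it through.** **1. The plan's own figure.** The documents give no power or variability for plasma DMA. The only design figure is for 24-hour urinary NDMA (SAP 3.2), and it reproduces. With difference ln 2 = 0.693, SD of the paired log difference sqrt(ln(1 + 1^2)) = 0.833 and one-sided 0.05, 14 pairs give 90.4% power (13 give 88.1%). Enrolment is 14/(1 - 0.2) = 17.5, so 18. None of this depends on plasma DMA.

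**2. Which scale is tested.**

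| Path in SAP 7.3.2 | Quantity tested | Matches the geometric summary? |
|---|---|---|
| Assumptions pass on raw values | arithmetic mean difference | no |
| Fail raw, pass log | geometric mean ratio | yes |
| Fail both | signed-rank shift | no |

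**3. Can the quantities disagree?** For log-normal data the arithmetic mean is the geometric mean times sqrt(1 + CV^2). The arithmetic ratio is therefore the geometric ratio times sqrt((1 + CV_ranitidine^2)/(1 + CV_placebo^2)). With equal CVs the two ratios coincide. With a geometric ratio of 1 and an assumed placebo CV of 30%:

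- ranitidine CV 50%: sqrt(1.25/1.09) = 1.07;
- ranitidine CV 80%: sqrt(1.64/1.09) = 1.23.

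So they can disagree on whether there is an effect, but only if variability differs between treatments.

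**4. How often, and at what cost.** All inputs are assumptions, because the documents give none for DMA: 18 log-normal pairs, within-subject CV 20-50%, between-subject CV 30-60%, true ratio 1.0-1.4 and one-sided 0.05 (SAP 7.3.2 states neither alpha nor sidedness). Levene's step is left out. The SAP does not say whether Shapiro-Wilk is applied to paired differences or to each treatment's values, so both readings were simulated. Loss is fixed-log power minus power of the planned rule.

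| Within / between CV, ratio | Shapiro-Wilk on | Raw scale kept | Planned rule | Fixed log | Loss (points) |
|---|---|---|---|---|---|
| 30% / 60%, 1.4 | differences | 56% | 91.7% | 94.5% | 2.8 |
| 50% / 60%, 1.4 | differences | within 53-87% | 62% | 67% | 5 |
| 30% / 60%, 1.2 | differences | within 53-87% | 51% | 55% | 4 |
| 30% / 60%, 1.4 | each treatment | 21% | 94.5% | 95.3% | 0.8 |
| 50% / 60%, 1.4 | each treatment | 8% | 66.1% | 66.6% | 0.5 |
| 30% / 60%, 1.2 | each treatment | 19% | 56.3% | 57.1% | 0.8 |

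The two readings come from separate runs, so fixed-log power differs slightly between them; the losses are within-run.

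Over all settings:

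- **Paired differences:** the raw scale is kept in about 53-87% of trials. The loss is up to about 5 points. In up to about 9-10% of trials the raw test is kept and gives the opposite significance call to the log test.
- **Each treatment's values:** the raw scale is kept in about 8-56% of trials. The loss is about 1 point or less in most settings. The largest found is 83.2% - 81.0% = 2.2 points (within 20%, between 60%, ratio 1.2). Opposite calls with the raw test kept occur in at most about 4%.
- Type I error stays near 5% under both readings, with equal variability in the two treatments.

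**The case against.** The case for leaving the rule alone is fair in several respects.

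- The rule is written in advance, keeps type I error in these simulations, and has both a log step and a nonparametric fallback. That stands.
- A reader might infer that the reported treatment effect differs from the tested one. The SAP plans no plasma effect estimate or interval, only summaries by treatment and a test. The mismatch is between those summaries and the test, and it disappears when the raw scale fails and the log scale passes.
- A reader might infer a larger power cost by comparing an always-raw t-test with the log test (88.5% against 94.5% in the first row of the table). The SAP does not plan an always-raw test. Mentioning Levene's test, which compares groups, makes it at least plausible that normality is to be checked treatment by treatment, and then the power argument nearly vanishes.
- Eighteen pairs is optimistic for AUC0-inf, which needs at least three terminal points and adjusted R-squared above 0.80.
- Urine DMA is not a perfect model to copy, because section 7.3.1 also switches to Wilcoxon.

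What survives is narrower: section 7.3.2 fixes a geometric summary for DMA, leaves the test scale to the data, and does not say what the normality test is applied to.

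**Conclusion.** The inconsistency is in the text and is minor. For plasma DMA the tested quantity is chosen by the data, parameter by parameter and meal by meal, and may match neither the geometric means reported with it nor the urine DMA test.

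The cost is mainly in interpretation. Under the assumed log-normal data and CVs, the planned rule loses up to about 5 points of power on one reading of the normality check and about 1 to 2 points at most on the other. These sizes depend on assumptions that the documents can neither confirm nor contradict.

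The documents do not support reading this as a threat to the trial's conclusion. The primary endpoint is urinary NDMA and the sample size was set for it. Of the two plasma parameters compared, only AUC0-inf is a named exploratory endpoint (SAP 4.2); Cmax is not.

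**What to change.** In SAP 7.3.2, for DMA:

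- log-transform AUC0-inf and Cmax in advance;
- test the paired log differences against 0, stating alpha and sidedness;
- report the geometric mean ratio with its interval for A against B and C against D;
- delete the Shapiro-Wilk step that chooses the scale;
- keep Wilcoxon as a labelled sensitivity analysis.

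In SAP 7.3.1, treat the Wilcoxon switch for urine DMA the same way. Otherwise plasma and urine DMA could still end on different scales.

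The cost is a few sentences and a small code change, with no new data. The effect would be read as a ratio rather than in concentration units, which fits the geometric means already planned. The log scale needs non-zero values, and SAP 6.1 sets results below the quantification limit to zero. The planned geometric means and the urine DMA analysis already carry that requirement.

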3.2 Sample Size

Eighteen healthy participants are planned for enrollment. It is estimated that a sample size of 14 completing subjects will provide at least 90% power at a 0.05 significance level to demonstrate an increase in 24-h urinary excretion of NDMA with ranitidine compared to placebo for a 1-sided log-transformed paired comparison. This assumes that geometric mean ratio between 24-h urinary NDMA with ranitidine and placebo is 2 and that the coefficient of variability is 100%. Enrolling 18 subjects allows for up to 20% dropouts.

Sample size calculations for the study are based on results from Zeng and Mitch (2016), which showed a 400-fold increase in NDMA for 150 mg ranitidine compared to placebo (47,600 ng versus 110 ng, respectively). The observed 24-h urinary excretion of NDMA with placebo for this and other studies ranged between 11-380 ng. It is not known if 24-h urinary excretion of NDMA with placebo is higher than what has been historically observed or if the fold-increase observed in Zeng and Mitch with ranitidine would be observed in a study controlling for meals with a randomized crossover design. The study sample size reflects assumptions that the overall fold-increase may be substantially lower but is still powered to detect an increase with assumptions as stated above.

4. Study Endpoints

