4.2 Exploratory Endpoints

The exploratory endpoints of this study are:

1. AUC from time 0 extrapolated to infinity (AUC_{0-inf}) of plasma ranitidine, NDMA and DMA
2. Cumulative ranitidine and DMA amount excreted in urine over 24 h after ranitidine administration

5. Analysis Populations

The PK population will include all subjects who receive study drug and have at least one on-treatment sample. The safety population will include all subjects who receive at least 1 dose of any of the study drugs. The analysis population will include all subjects in the PK population with sufficient data to calculate PK parameters from at least two study periods of the same meal

type (i.e., low nitrite/NDMA or high nitrite/NDMA). Treatment in all analysis populations will be assigned based upon the treatment which the subjects actually received.

6. Data Screening and Acceptance

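### SAP 7.3.2 makes the plasma paired t-test conditional on Levene's test, a condition the paired t-test does not have, so a valid planned test is dropped more often as the drug effect grows

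*SAP*

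**What the plan says.** SAP 7.3.2 compares plasma AUC0-inf and Cmax between ranitidine and placebo separately for the low and high nitrite/NDMA meals (A with B, C with D). The sentence ends "comparison between Treatments C and D, respectively) using a paired t-test".

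Three rules follow, in this order:

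- Normality is checked with Shapiro-Wilk: "If the assumption is not valid, the data will be log-transformed, and then tested for normality".
- Equal spread is checked as well: "Homogeneity of variances will be verified using Lavene's test".
- The fallback is: "If the data in its original or transformed form does not meet the t-test assumptions, a Wilcoxon signed-rank test will be used for the comparison".

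Equal variance is thus treated as one of the t-test's assumptions, and failing it can remove the planned test. The section does not give a significance level for the checks. Nor does it say whether they apply to the treatment values or to the within-subject differences, or whether a Levene failure, as opposed to a normality failure, leads to the log scale.

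On status, SAP 4.2 lists "AUC from time 0 extrapolated to infinity (AUC_{0-inf}) of plasma ranitidine, NDMA and DMA" among the exploratory endpoints. Cmax is not a listed endpoint. Protocol 4.9.6.2 plans only descriptive plasma summaries. Plasma ranitidine parameters are derived for A and C only, so the paired comparisons concern NDMA and DMA.

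**The concern.** A paired t-test is a one-sample t-test on the within-subject differences. Its distributional requirement is on those differences. The ranitidine and placebo values may have any two variances without breaking it.

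Levene's test needs at least two groups, so here it can only compare the spread of the ranitidine values with that of the placebo values. It assumes the groups are independent, but these come from the same subjects.

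Concentration data often have an SD that rises with the mean. If ranitidine raises the mean, it then also raises the spread, and Levene's test becomes likely to reject because there is an effect. The planned test would be retained when nothing happens and replaced when something does. The signed-rank test addresses a different hypothesis: symmetry of the differences about zero, not a zero mean difference. At stake are which test and hypothesis are reported for the plasma comparisons, and whether the two meal types end on the same one.

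**Working it through.** **Pair counts, and the plan's own figure.** The SAP gives no power or variability figure for plasma. The pair counts come from SAP 3.2, which concerns urinary NDMA: "Eighteen healthy participants are planned for enrollment", and "a sample size of 14 completing subjects will provide at least 90% power at a 0.05 significance level". That figure reproduces. With a ratio of 2, delta = ln 2 = 0.693. With a CV of 100% taken as setting the SD of the log difference, SD = sqrt(ln(1 + 1²)) = 0.8326. At n = 14 the noncentrality is sqrt(14) × 0.693/0.8326 = 3.11, and one-sided paired-t power at 0.05 is 90.4% (88.1% at n = 13). Allowing for 20% dropout, 14/0.80 = 17.5, rounded up to 18. This fixes 14 to 18 pairs as the working range and has no other bearing on the point.

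**Assumptions not in the documents.** Both checks are at 0.05, Levene is median-centred, and Shapiro-Wilk is on the within-subject differences. The plasma CVs and correlations are also assumed.

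**Step 1: does unequal variance harm the paired t-test?** Bivariate normal pairs with equal means, SD ratios 1, 2, 4 and 10, correlations 0 to 0.9:

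| SD ratio | Levene rejects, n = 14 | Levene rejects, n = 18 |
|---|---|---|
| 2 | 48-50% | 66-75% |
| 4 | 97-99% | 99-100% |

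The one-sided type I error of the paired t-test stays at 4.8-5.2% for a nominal 5% at every SD ratio. The gate fires, and the test it guards is sound.

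**Step 2: does Levene's test fit paired periods?** With equal variances and correlation 0.9 it rejects in 0.0-0.2% of trials instead of 5%. Its own level is not maintained.

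**Step 3: how often does Levene alone force the switch?** 18 normal pairs, CV 30%, SD proportional to the mean, correlation 0, 0.5 or 0.8. A switch is counted when Levene rejects and the differences pass Shapiro-Wilk.

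| True ratio | Log scale tried only after a normality failure | Log scale also tried after a Levene failure |
|---|---|---|
| 1 | about 3% or less | lower still |
| 1.5 | 18-26% | 3-5% |
| 2 | 62-69% | 10-14% |
| 3 | 91-95% | 17-19% |

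With 14 pairs, the middle column is 12-20%, 46-48% and 83-89% at ratios 1.5, 2 and 3.

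**Step 4: a different data model.** Lognormal pairs with a purely multiplicative effect, between/within CV from 20/10% to 60/60%, n = 14 and 18, run through the 7.3.2 sequence with the log step tied to normality. The switch to Wilcoxon, for any reason, rises from 3-6% with no effect to 14-56% at 2-fold and 29-89% at 4-fold. On the log scale Levene rejects in only 0.1-2.6%.

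**Step 5: does the switch change conclusions?** In the Step 3 setting, two-sided at 0.05, power at 1.5-fold and correlation 0 is 96.3% (t-test), 95.4% (Wilcoxon) and 96.0% (gated procedure). It is at least 99.7% at 1.5-fold with higher correlation and 100% at 2-fold and 3-fold. With equal means, SD ratios 1, 2 and 4 and correlation 0.5, the gated procedure's type I error is 4.6-5.5%. After a Levene-only switch, the two tests disagree on significance in at most about 1% of trials.

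**Step 6: can the two meals end on different tests?** The gates run separately. If both meals had a 2-fold effect and the gates acted independently (a simplification, since the subjects are the same), the chance of a split is 2p(1 − p). For p = 0.62 this is 2 × 0.62 × 0.38 = 0.47, and for p = 0.69 it is 2 × 0.69 × 0.31 = 0.43. Under the log-retry reading, p = 0.10 gives 0.18 and p = 0.14 gives 0.24.

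**The case against.** The strongest reply is that nothing of inferential weight is lost. The fallback is pre-specified and is itself a paired test, and Step 5 shows that error rates and power are nearly the same. This stands. A reader might infer that the gate inflates type I error or costs power; the calculations do not support that.

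Second, the fallback clause refers to the data in original or transformed form, which can be read as trying the log scale before giving up the t-test. This also stands as a possible reading. It cuts the rates to the last column of the Step 3 table but does not remove them. The sentence that introduces the log step ties it to normality alone.

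Third, the inputs are assumed. For NDMA, SAP 6.1 sets values below the quantification limit to zero, and the SAP change log reports many such samples, including whole periods for multiple subjects. Normality may then fail before Levene matters, and logs of zero are unavailable. SAP 7.3.2 also restricts AUC0-inf to profiles with at least three terminal points and adjusted R² above 0.80, so the number of pairs may be smaller. The point is therefore clearest for DMA.

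Two further inferences go too far. One is that a planned mean difference or ratio is lost: 7.3.2 names no difference, ratio or interval for plasma, unlike the urine rule in 7.3.1. The other is that the meal conditions could no longer be compared: the mean, SD, CV, median and range are reported whichever test is used, so only the p-values might come from different tests.

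**Conclusion.** The point holds as a correction to the test rule. SAP 7.3.2 checks a condition the paired t-test does not require, with a test that does not suit paired data, and can discard a valid planned test on that ground. The chance of doing so grows with the drug effect: under the Step 3 assumptions, from about 3% or less with no effect to 62-69% at 2-fold, or 10-14% at 2-fold if the log scale is tried first. The documents do not settle which reading applies and give no plasma variability, so these rates show direction and rough scale and do not predict this trial.

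The consequence is limited to an effect-dependent change in which test and hypothesis are reported for exploratory plasma parameters, possibly differing between the two meals. A reader might extend this to the primary endpoint. The documents do not support that: urinary NDMA is analysed under 7.3.1, by an ANOVA with its own assumption rule, which is a separate question. The change is worth making but minor.

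**What to change.** Delete the Levene sentence from SAP 7.3.2. State that Shapiro-Wilk is applied to the within-subject differences, on the original scale first and then on the log scale where the SAP's existing log step applies. State that only non-normality of those differences leads to the signed-rank test.

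This leaves the SAP's scale rule as it is. Hard-wiring the original scale for NDMA and the log scale for DMA would be a different and larger change, because the arithmetic/geometric split in 7.3.2 governs descriptive summaries and not the tests.

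The cost is one sentence removed and a clarification added. No needed safeguard is lost: without the gate the paired t-test holds its level (Step 1), and Levene-driven switching falls to zero.
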